9.5.5 Clinical Response Parameters

Progression is a composite endpoint defined from the Prostate Cancer Working Group 2 (PCWG2) criteria for metastatic castrate resistant prostate cancer (mCRPC) (75) and our previous trials in a population of men with biochemical failure without metastases (72-74). Progression will be defined as either: 1) a $\geq 25\%$ increase in PSA from nadir (and by ≥ 2 ng/mL), requiring confirmation ≥ 4 weeks later (PCWG2 criteria); and/or, 2) clinical/radiographic-progression defined as symptomatic progression (worsening disease-related symptoms or new cancer-related complications), or radiologic progression (on CT scan: $\geq 20\%$ enlargement in sum diameter of soft-tissue target lesions [RECIST 1.1 criteria]; on bone scan: ≥ 1 new bone lesions), initiation of ADT or death due to any cause, whichever occurs first. Death is considered a severe adverse event here.

Progression Free Survival (PFS) is defined as the time from starting treatment to the time of progression as defined above. Subjects who do not progress will be censored at the time of the last contact.

ADT Free Survival (ADT-FS) is defined as the time from starting treatment to the time of initiation of palliative ADT. ADT will typically be initiated on tumor progression and/or development of new metastases. Subjects who do not start ADT will be censored at the time of the last contact.

Time to Progression (TTP) is defined as the time from starting treatment to the time of first documented tumor progression or new lesions by CT and/or bone scan or initiation of ADT. Subjects who do not progress will be censored at the time of the last contact. In addition, death from any cause will also be censored.

Time to New Metastasis (TNM) is defined as the time from starting treatment to the time of a new documented tumor metastasis by CT and/or bone scan. Subjects who do not progress will be censored at the time of the last contact.

Overall Survival (OS) is defined as the time from starting treatment until death due to any cause. For subjects who do not die, time to death will be censored at the time of last contact.

Locoregional Control (LRC) is defined as the time from starting treatment until local and/or regional relapse is documented

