CORRELATIVE SCIENCE	
• To enumerate circulating tumor cells (CTC) using EPIC HD-CTC platforms at baseline, months 3, 6 and 12 from randomization.• To enumerate circulating tumor DNA (ctDNA) using Cancer Personalized Profiling by deep sequencing (CAPP-Seq) at baseline, months 3, 6 and 12 from randomization for SABR versus SABR + Radium-223.• To quantitatively sequence T-cell receptor (TCR) repertoires using peripheral blood monocytes and the ImmunoSEQ platform at baseline, months 3, 6 and 12 from randomization.• To evaluate immunophenotypes by running PBMCs through a Cytek Aurora machine, which allows for simultaneous detection of up to 25 markers; to evaluate metabolic fitness of the total PBMCs using the mitochondrial stress test on the Seahorse analyzer; and to determine the relative capacity of peripheral T cells to metabolically respond to T cell receptor stimulation through activation of CD3 and CD28 by running functional assays on PBMCs.• To determine frequency of germline DNA repair mutations in the oligometastatic state• Descriptive statistics will be performed to correlate the metrics above with clinical outcomes.
HYPOTHESES	SABR + Radium-223 will increase median progression-free survival from 10 months in the SABR arm to 20 months in the SABR + Radium-223 arm
STUDY DESIGN	Men with oligometastatic prostate cancer lesions will be randomized (1:1) to SABR versus SABR + Radium-223. The study will NOT be blinded. Within three weeks of the initial treatment planning, SABR(1-

	5 fractions) will be administered for all men. For the SABR + Radium-223 the 1 st radium-223 infusion will be within four weeks from randomization.
SAMPLE SIZE BY TREATMENT GROUP	64 patients total
SUMMARY OF SUBJECT ELIGIBILITY CRITERIA	
 1. Metastatic bone or nodal sites \leq 3 on standard imaging (or \leq 5 on Axumin, Choline with at least one bone metastasis. 2. PSA DT $<$ 15 months 3. Tumor \leq 5.0 cm or $<$ 250 cm³. 4. Age \geq 18 years. 5. ECOG performance status \leq 2. 6. Histologic confirmation of malignancy (primary or metastatic tumor).
CONTROL GROUP	N/A

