5.1 Inclusion Criteria

- 5.1.1 Patient must have at least one and up to three asymptomatic metastatic tumor(s) of the bone or soft tissue (with at least one bone metastasis) within the past 3-months that are ≤ 5.0 cm or <250 cm 3 as seen on either CT/MRI scan and/or bone scan. Up to five lesions are allowed on advanced functional imaging such as fluciclovine (Axumin), choline or ^{18}F -DCFPyL (“PyL”) PET-CT scan within the past 6-months. (PET-CT scan is reasonable for study entry imaging as an alternative to CT/MRI scan and/or bone scan)
- 5.1.2 Patient must have had their primary tumor treated with surgery and/or radiation.
- 5.1.3 Histologic confirmation of malignancy (primary or metastatic tumor).
- 5.1.4 PSADT <15 months. PSA doubling time (PSADT) will be calculated using as many PSA values that are available from time of relapse (PSA > 0.2). To calculate PSADT, the Memorial Sloan Kettering Cancer Center Prostate Cancer Prediction Tool will be used. It can be found at the following web site: <https://www.mskcc.org/homograms/prostate/psa-doubling-time>.
- 5.1.5 Patient may have had prior systemic therapy and/or ADT associated with treatment of their primary prostate cancer. Patient may have had ADT

associated with salvage radiation therapy (to the primary prostate cancer or pelvis is allowed).

5.1.6 PSA ≥ 0.5 but ≤ 50 .

5.1.7 Any testosterone lab within the past 6 months $> 50\text{ng/dL}$.

5.1.8 Patient must be ≥ 18 years of age.

5.1.9 Patient must have a life expectancy ≥ 12 months.

5.1.10 Patient must have an ECOG performance status ≤ 2 .

5.1.11 Patient must have normal organ and marrow function as defined as:

Before the first administration of Xofigo, the absolute neutrophil count (ANC) should be $\geq 1.5 \times 10^9/\text{L}$, the platelet count $\geq 100 \times 10^9/\text{L}$ and hemoglobin $\geq 10 \text{ g/dL}$.

5.1.12 Patient must have the ability to understand and the willingness to sign a written informed consent document.

5.1.13 LDH lab performed within 6 months of enrollment.

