9. MEASUREMENT OF EFFECT

9.1 Antitumor Effect – Metastatic Tumors

For the purposes of this study, patients should be re-evaluated for radiographic response 6- and 12-months after randomization. Trial radiologists evaluating for treatment responses will be blinded to the treatment group and treatment specifics (lesions treated with SABR).

Response and progression will be evaluated in three ways:

- 1) Using Response Evaluation Criteria in Solid Tumors (RECIST 1.1) Committee definition. Changes in only the largest diameter (uni-dimensional measurement) of the tumor lesions are used in the RECIST criteria.
- 2) Lesions by bone scan will be evaluated as positive, negative or no change. MRI of the bone lesion can be used to clarify equivocal lesions.
- 3) Serial PSA changes.

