9.5.6 Response Review

All responses will be reviewed by the study co-investigator radiologists.

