10.3 Potential Adverse Events

Signs and symptoms of disease progression are not considered AEs. The development of a new cancer should be regarded as an AE. New cancers are those that are not the primary reason for administration of study treatment and have been identified after inclusion of the patient into the clinical study.

Because patients are receiving standard treatments, which are not part of this study, their treating physician will be counseling them on the risk of their treatments, including the risk of surgery, radiation therapy, and/or chemotherapy, whichever is appropriate for the type and the stage of their cancer. The procedures related to the study are phlebotomy, SBRT, and Radium-223 administration.

Phlebotomy can cause pain, bleeding, and rare needle site infection.

Reporting: All patients will be seen during the required protocol and calendar time-points, by their radiation oncologist or study team member, during the entirety of the trial. Any observations during the entirety of the study (2 years) will be recorded and should include attention toward the following potential side effects:

- Anal hemorrhage, colitis, constipation, diarrhea, fecal incontinence, hemorrhoids, nausea, proctitis, rectal hemorrhage, vomiting
- Anorexia, anxiety, and/or insomnia
- Bladder spasms, hematuria, urinary frequency, urinary incontinence, urinary retention, urinary tract pain, urinary urgency, erectile dysfunction
- Dermatitis radiation
- Fatigue and/or pain
- Hot flashes
- Bone Pain
- Neutrophil count decrease and/or platelet count decrease

Any and ALL additional adverse events should be recorded, even if not listed in the above potential side effects.

10.4 Stereotactic Body Radiation Treatment (SBRT)/Stereotactic Ablative Radiation Treatment (SABR)

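### The symptom limb of the primary PFS event needs no persistence or corroboration and is judged open label; a counting rule and a sensitivity analysis would cheaply limit misclassification

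*Combined protocol and SAP*

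**What the plan says.** Section 5.1.1 sets the starting state: "Patient must have at least one and up to three asymptomatic metastatic tumor(s) of the bone or soft tissue", with at least one bone metastasis. The synopsis states: "The study will NOT be blinded".

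Section 9.5.5 defines progression as a composite in which any single limb is enough. The PSA limb has a relative threshold and an absolute one, "requiring confirmation ≥ 4 weeks later (PCWG2 criteria". The imaging limb has numeric or new-lesion criteria. The symptom limb reads: "clinical/radiographic-progression defined as symptomatic progression (worsening disease-related symptoms or new cancer-related complications". No instrument, size of change, duration, repeat assessment or attribution procedure follows.

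Blinding and review are described for images only. Section 9.1 says: "Trial radiologists evaluating for treatment responses will be blinded to the treatment group and treatment specifics (lesions treated with SABR". Section 9.5.6 says: "All responses will be reviewed by the study co-investigator radiologists". No one blinded to the arm is assigned to judge symptoms.

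Section 10.3 says: "Signs and symptoms of disease progression are not considered AEs". The same section lists fatigue, pain and bone pain among the potential side effects to watch for, and gives no rule for telling the two apart. The Brief Pain Inventory is collected, but 14.5 uses it only for quality of life. Section 14.4 adds no rule on symptoms and points for the definition of progression to a section 9.6.2 that the document does not contain.

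**The concern.** For men who enter without symptoms from their metastases, any new symptom judged to come from the cancer is a worsening. A transient one qualifies at once, because nothing requires it to last. The same new bone pain can be filed as an adverse event or as a primary endpoint event, and the choice is made by someone who knows whether radium-223 was given.

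Two things are at stake. False events that are equally common in both arms pull the hazard ratio toward 1 and cost power. False events that are called more often in one arm bias the comparison. The test is one-sided at 0.10 with about 38 expected events, so two or three misclassified men can matter.

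**Working it through.** **Inputs from 14.2.** 30 men per arm, 1:1; median PFS 10 v 20 months (hazard ratio 0.5); one-sided log-rank test at 0.10; 18 months of accrual plus 12 months of follow-up; 80% power; 5% drop-out, giving 64.

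**Reproducing the plan's figure.** Assume exponential PFS and uniform accrual.
- Monthly hazards: ln2/10 = 0.0693 and ln2/20 = 0.0347.
- Event probability for hazard λ: P = 1 − [exp(−12λ) − exp(−30λ)]/(18λ). This gives 0.751 (SABR) and 0.509 (SABR + radium-223).
- Expected events: d = 30 × (0.751 + 0.509) = 37.8.
- Power = Φ(½√d × |ln HR| − 1.2816) = Φ(3.075 × 0.693 − 1.2816) = Φ(0.85) = 0.802. A log-rank simulation gives 0.798.
- 60/0.95 = 63.2, rounded up to 64.

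The stated 80% and 64 reproduce.

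**Adding false symptom events.** The documents give no rate, so a cumulative 12-month false-event probability r is assumed. It enters as an extra hazard f = −ln(1 − r)/12.

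Worked example, r = 10%: f = −ln(0.9)/12 = 0.00878.
- Equal in both arms: HR = (0.03466 + 0.00878)/(0.06931 + 0.00878) = 0.556; d = 41.3; power = Φ(½√41.3 × 0.587 − 1.2816) = 0.727.
- SABR alone only, no true effect: apparent HR = 0.06931/0.07809 = 0.888; d = 46.2; one-sided error = Φ(½√46.2 × 0.119 − 1.2816) = 0.19. This corresponds to about 2.7 false first events among 30 men.

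| Assumed r by 12 months | Both arms: HR | Both arms: power | SABR alone only, no true effect: one-sided error |
|---|---|---|---|
| 0 | 0.500 | 0.802 | 0.10 |
| 1% | 0.506 | 0.795 | 0.11 |
| 3% | 0.518 | 0.780 | 0.12 |
| 5% | 0.529 | 0.765 | 0.14 |
| 10% | 0.556 | 0.727 | 0.19 |

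Log-rank simulations give power of 0.769 and 0.713 for 5% and 10% in both arms, and an error of 0.19 for 10% in SABR alone only. A less extreme imbalance, 10% in SABR alone v 5% in the radium arm, gives an error of 0.14. In the other direction, false events only in the radium arm with a true hazard ratio of 0.5 leave power at 0.70 (5%) or 0.58 (10%). Nothing in the documents says which direction, if either, applies.

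**The case against.** Several points on the other side stand.

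- **Attribution.** A reader might infer that treatment-related pain counts as progression. It does not: the limb is restricted to disease-related symptoms, so such pain enters only by misattribution. Sections 10.2.4 and 10.5.1.1 provide a five-level attribution scale and a causality rating. However, these apply to events recorded as adverse events, and 10.3 removes progression symptoms from that category.
- **Corroboration is possible.** Section 6.7.2 allows imaging outside the 6- and 12-month schedule when clinical findings call for it. This permits a check but does not make the event depend on it.
- **Symptom-only events may be rare.** Section 4.5 reports that, in an earlier randomized trial of metastasis-directed therapy, the three men who started ADT purely for symptomatic progression were all under surveillance. Here both arms receive SABR. That is indirect, because it counts ADT starts, but it favours the low end of the assumed range.
- **Radium-specific bone pain.** A reader might expect more false events in the radium arm from this source. The only comparative figure runs the other way: serious bone pain in 10% on radium-223 v 16% on placebo (4.4 and its continuation), in a different, symptomatic population.
- **Planning medians.** Section 14.2 ties its progression rate to the composite definition, so the 10-month median may already include some such events. Adding a further hazard could count them twice.
- **Margin.** Following every man for 24 months gives 30 × [(1 − exp(−24 × 0.0693)) + (1 − exp(−24 × 0.0347))] = 41 events and power of 0.83 on the design hazards. Imaging after month 12 is discretionary, so this is an upper view.

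None of this supplies a persistence or corroboration rule for the symptom limb, or a blinded judge of it.

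**Conclusion.** The gap is real and limited. As written, an unconfirmed symptom judgement made open label can be a primary PFS event, while the PSA limb needs confirmation and the images are read blind. The size is unknown. Under assumed equal false rates of 1% to 10%, the power loss runs from under 1 point to about 7.5 points, and at 1% to 3% it is about 1 to 2 points. The error figures of 0.11 to 0.19 require all false events to fall in the SABR-alone arm, which no document shows. All of these rest on exponential PFS, a constant false-event hazard and planning medians free of such events.

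The documents do not support reading this as a demonstrated bias for or against radium-223, or as an error in the sample size, which reproduces as stated. It is a cheap improvement to the endpoint definition.

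**What to change.** Add to 9.5.5 and 14.4 a rule used only for counting PFS events. It should state that it does not change when a man may leave study treatment or start other therapy, because 6.11, 6.12 and 6.15 use progression for those decisions.

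1. Count a symptom-only event when imaging or PSA supports it, or when a later contact documents that it persists. Date it at first onset.
2. Record in the CRF which limb triggered each PFS event.
3. Pre-specify a sensitivity analysis of PFS that excludes symptom-only events. ADT start, death, PSA progression and radiologic progression still count.
4. State whether new cancer-related complications without imaging or PSA support are handled as symptom-only, and correct the reference to 9.6.2.

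If a Brief Pain Inventory threshold is wanted, the sponsor should choose and justify it. The instrument covers pain only and is completed by a man who knows his arm.

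The cost is protocol and SAP wording, one CRF field and sometimes one extra contact, for which section 8 already allows telemedicine. A few true symptom-only events may be missed, although a man who starts ADT before confirmation still counts through that limb. The sensitivity analysis also depends on PSA and imaging data continuing after a symptom call. If a man leaves the study at that point, his censoring may be informative, so the number of such men should be reported by arm.

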9.5 Response Criteria

9.5.1 Evaluation of Target Lesions/PSA Response

Complete Response (CR): Disappearance of all target lesions and PSA $<$ pre-SBRT PSA

Partial Response (PR): At least a 30% decrease in the sum of the longest diameter (LD) of target lesions, taking as reference the baseline sum LD. Or a third of the lesions are negative or no change by bone scan and PSA \leq pre-SBRT PSA.

Progressive Disease (PD): At least a 20% increase in the sum of the LD of target lesions, taking as reference the smallest sum LD recorded since the treatment started or the appearance of ≥ 1 new lesion(s). Or ≥ 1 new lesion(s) appear by bone scan. Or PSA $\geq 25\%$ increase in PSA from nadir or > 50 ng/ml.

Stable Disease (SD): Neither sufficient shrinkage to qualify for PR nor sufficient increase to qualify for PD, taking as

reference the smallest sum LD since the treatment started. Or PSA \geq pre-SBRT PSA, but not $\geq 25\%$ increase in PSA from nadir and <50 ng/ml.

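### The primary PFS event is defined inconsistently: the radiologic list in 9.5.5 omits new extra-osseous lesions that 9.5.1, TTP and TNM count, and 14.4 cites a section 9.6.2 that does not exist

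*Combined protocol and SAP*

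**What the plan says.** - **9.5.5, progression (used for PFS).** A confirmed PSA rise; symptomatic progression; on CT at least 20% "enlargement in sum diameter of soft-tissue target lesions [RECIST 1.1 criteria]; on bone scan" at least one new bone lesion; ADT start; or death.
- **9.5.1, PD.** Growth of at least 20% relative to "the smallest sum LD recorded since the treatment started or the appearance of" at least one new lesion. A separate item then adds the case where "new lesion(s) appear by bone scan".
- **9.5.5, TTP.** The event is "first documented tumor progression or new lesions by CT and/or bone scan or initiation of ADT".
- **9.5.5, TNM.** The event is "a new documented tumor metastasis by CT and/or bone scan".
- **9.1.** Response and progression are to be evaluated "Using Response Evaluation Criteria in Solid Tumors (RECIST 1.1) Committee definition", together with bone scan and serial PSA.
- **14.4.** For the definition of progression, the primary analysis refers to section 9.6.2. Section 9 ends at 9.5.6 and section 10 follows. Sections 6.11 and 6.15 refer to 9.5.5.

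**The concern.** PFS is the primary endpoint, and about 38 events are expected. The documents give two answers to a basic coding question: is a new node, soft-tissue deposit or visceral lesion on a scheduled CT/MRI a PFS event? Two analysts working from the same scan could date the primary event differently, or disagree on whether it has occurred. Such lesions are foreseeable, since 5.1.1 admits men with soft-tissue metastases alongside bone disease.

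The broken reference leaves two candidate sections. They differ on new CT lesions and also on PSA. Treatment is open-label, so settling the question after outcome data have been seen would be a data-dependent choice about the primary endpoint.

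**Working it through.** **1. The passages side by side**

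| Finding | PFS, 9.5.5 literal | PD, 9.5.1 | TTP | TNM |
|---|---|---|---|---|
| New bone lesion on bone scan | event | event | event | event |
| Soft-tissue target growth of at least 20% | event | event | event | no |
| New extra-osseous lesion on CT | **not listed** | event | event | event |

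Take a man whose month-6 CT shows one new node. He has no target growth, no new bone lesion, no qualifying PSA rise, no symptoms and no ADT. TTP and TNM end at month 6. PFS, which 9.5.5 counts from the same treatment start, runs on. A composite that includes death and PSA should not outlast TTP.

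Nothing else in section 9 closes the gap: 9.3 and 9.5.2 mark non-target lesions as not applicable.

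**2. The two candidate PSA rules**

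Section 9.5.5 needs a 25% rise from nadir, an absolute rise of at least 2 ng/mL, and confirmation at least 4 weeks later. Section 9.5.1 needs only the 25% rise, and adds a limb for PSA above 50 ng/ml. The 2 ng/mL minimum binds whenever the nadir is below 2 / 0.25 = 8 ng/mL.

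**3. The plan's own power (14.2)**

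Inputs: medians of 10 and 20 months, HR 0.5, one-sided alpha 0.10, 30 per arm, 18 months of accrual plus 12 of follow-up. I assume exponential PFS and uniform accrual.

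- P(event) = 1 − [exp(−12λ) − exp(−30λ)] / (18λ), which gives 0.751 (λ = ln2/10) and 0.509 (λ = ln2/20).
- Expected events = 30 × (0.751 + 0.509) = 37.8.
- Power = Φ(√(37.8/4) × ln 2 − 1.2816) = 0.802.

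The stated 80% reproduces.

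**4. What counting these lesions could cost (illustration)**

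Let f be the share of the full-progression control hazard made up of first events that are only new extra-osseous lesions. Let h be the radium-223 hazard ratio on them. Neither is in the documents. The HR on the narrow list is held at 0.50, and these lesions are treated as not captured by any other limb. Then HR for full progression = 0.5(1 − f) + h·f.

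Power is shown for two cases. In A the 10-month median already counts these lesions. In B it does not, so the control hazard becomes (ln2/10)/(1 − f).

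| f | h | HR | Power, A | Power, B |
|---|---|---|---|---|
| 5% | 1 | 0.525 | 76.2% (38.3 events) | 77.0% (39.4 events) |
| 5% | 0.75 | 0.5125 | 78.2% | 79.1% |
| 5% | 0.5 | 0.50 | 80.2% | 81.0% |
| 10% | 1 | 0.55 | 71.9% (38.8 events) | 73.6% (40.9 events) |
| 10% | 0.75 | 0.525 | 76.2% | 77.9% |
| 10% | 0.5 | 0.50 | 80.2% | 81.8% |

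The range is not bounded by these rows. With h = 1 in case A, a 20% share gives HR 0.60 and 62.9% power, and a 30% share gives HR 0.65 and 53.6%.

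**The case against.** The strongest reply is that the literal reading is not the natural one. Section 9.1 invokes RECIST 1.1 for progression, 9.5.1 counts new lesions, the CT limb of 9.5.5 carries a RECIST tag, and 14.4 speaks of progressive disease, the term defined in 9.5.1. On this view the list in 9.5.5 is shorthand, and 9.6.2 is a stale number for 9.5.5. This makes the broad reading plausible, and 9.5.5 is the likelier target. The conflict remains: the tag sits on target-lesion enlargement, and 9.5.5 spells out new CT lesions for TTP and TNM but not for PFS.

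The second reply is that little is lost in practice. Section 4.5 puts bone at over 90% as the major metastatic site. PSA is drawn at months 3, 6 and 12 (6.7.1), so at or before the month-6 and month-12 scans. ADT start is itself a PFS event, and "ADT will typically be initiated on tumor progression and/or development of new metastases". Scheduled CT/MRI covers only the metastatic sites (6.7.2), which limits how many such lesions are seen. This stands as a reason to expect a small effect. But the 90% figure is not a share of first progressions, and capture through ADT moves the event to the date ADT starts.

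A reader might go further and infer that the narrow list flatters radium-223, because the agent seeks bone (4.4). The documents give no effect of radium-223 on extra-osseous lesions and no share of such first events. If it acts equally on them, the HR does not change. Nor is there a case for inflated type I error or reader bias: the omission applies to both arms, and 9.1 states that "Trial radiologists evaluating for treatment responses will be blinded to the treatment group".

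**Conclusion.** The inconsistency is established from the text and should be fixed. The primary event has two readings, and the reference that should decide between them leads nowhere. Under the literal reading PFS can exceed TTP in the same patient.

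The size of the effect on the HR cannot be derived from the documents and may be small. A reader might also infer that the current text already costs power. That is not supported: 14.2 ties its planning rate to progression as defined earlier in the protocol, so the 80% may belong to either reading. The power figures above therefore price the fix rather than measure a present loss. They rest on assumed values of f and h, on exponential PFS, and on no capture through other limbs.

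**What to change.** - Give one event list for the PFS analysis. Make it agree with 9.5.1, TTP and TNM by counting at least one new nodal, soft-tissue or visceral lesion on CT/MRI as radiologic progression.
- State that the 9.5.5 PSA rule is the one used for PFS.
- Point 14.4 to that list in place of 9.6.2.
- Settle this before outcome data are examined, and confirm that the 10-month planning median and the 80% power refer to the same definition.

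No scan is added, because CT/MRI is already scheduled at months 6 and 12. Only new lesions within the imaged region will be found. The named downside is power: if radium-223 acts less on extra-osseous lesions, power falls somewhat below 80%, to 76–77% in the illustration with a 5% share and no effect, and further if the share is larger.

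The change is meant for the PFS analysis endpoint only. Sections 6.11 and 6.15 rely on 9.5.5 for removal and withdrawal. The sponsor must reconcile those passages separately, and no clinical rule is proposed here.

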14.1.2 Secondary Objectives

- To describe the toxicity of SABR and SABR + Radium-223 delivered for the population enrolled using grading with CTCAE v. 4.0
- To determine local control at 12-months after SABR and SABR + Radium-223 in patients with oligometastatic disease.

- To assess time to locoregional progression, time to distant progression, time to new metastasis and duration of response after randomization to SABR *versus* SABR + Radium-223.
- To assess ADT-free survival (ADT-FS) of this patient population after randomization defined as the time interval between the day of randomization and the initiation of ADT. ADT will typically be initiated on progression and/or development of new metastases.
- To assess quality of life following SABR *versus* SABR + Radium-223 arms. Brief Pain Inventory form which will be filled out by the patient at the treatment response intervals outlined above.

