14.2 Sample Size/Accrual Rate/Follow-Up

The primary endpoint will be progression-free survival (PFS). Data from STOMP and ORIOLE on this patient population indicate that $\geq 50\text{-}60\%$ would show progression as defined above within a 12-month period from SABR, and a median PFS around 10 months. (72-74). We hypothesize that the addition of radium-223 will be able to reduce the risk of progression by 50%. A sample size using a 1:1 randomization scheme of 30 patients per arm will provide 80% power to detect an increase of median PFS from 10 months to 20 month (corresponding to hazard ratio 0.5) with type I error = 0.1, using one-sided log-rank test. The calculation assumes 18 months of accrual time with an additional follow-up of 12 months after the last patient is randomized. To account for 5% early drop out, we will randomize a total of 64 patients (32 per arm).

There will be no interim analysis for futility, since the progression endpoint will not have been reached by a meaningful number of patients before full accrual.

Follow-up (Every 3-6 months for 24 months or until death)

Patients will be followed for 2 years after Day One of trial or until death. Patients withdrawn from the study because of AEs will be followed until the adverse event has either resolved or stabilized. Reasons for premature withdrawal should be determined and noted.

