14.5 Analysis of Secondary Objectives

- For safety analysis, adverse events will be summarized by type and grade.
- Kaplan-Meier (KM) estimates will be used to summarize ADT-free survival (ADT-FS), time to locoregional progression (TTLP), time to distant progression (TTDP), time to new metastasis (TNM) and duration of response over time. The median PFS, ADT-FS, TTLP, TTDP TNM and duration of response will be reported.
- The efficacy of SABR + Radium-223 in men with oligometastatic disease will also be determined by measuring local control of each lesion at 12-months.

Each metastatic lesion will be considered a target lesion and independently evaluated for response using RECIST 1.1 or bone scan evaluation criteria above. The lesion will be coded as being locally controlled if it is considered stable radiographic disease or if there is evidence of a partial or complete response. Local control assessment will start at three months following randomization and continuous assessment will be pursued during the follow-up period. The proportion of the lesions that have a stable or better response will be estimated using generalized estimating equation.

- Quality of life will be assessed using the Brief Pain Inventory form. An overall score will be calculated pre-treatment and at the time of the 2nd radiologic reassessment. The change in score will be evaluated with a paired t-test.

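### ADT-free survival does not count death as an event, so the planned Kaplan-Meier curve estimates time to ADT rather than survival free of ADT

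*Combined protocol and SAP*

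**What the plan says.** ADT-free survival (ADT-FS) is a secondary endpoint with two definitions.

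- Section 9.5.5: "ADT Free Survival (ADT-FS) is defined as the time from starting treatment to the time of initiation of palliative ADT". The censoring rule is "Subjects who do not start ADT will be censored at the time of the last contact".
- Section 14.1.2: "defined as the time interval between the day of randomization and the initiation of ADT". No censoring rule is given there.

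The clock starts at treatment in 9.5.5 and at randomization in 14.1.2. Neither definition mentions death.

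For the analysis, section 14.5 says "Kaplan-Meier (KM) estimates will be used to summarize ADT-free survival (ADT-FS" and lists several other time-to-event endpoints with it, with medians to be reported. It names no between-arm test for ADT-FS, no competing-risk method and no sensitivity analysis that counts deaths.

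Elsewhere 9.5.5 does deal with death. The progression composite ends with "initiation of ADT or death due to any cause, whichever occurs first", and overall survival has death as its event. Time to progression carries its own sentence: "In addition, death from any cause will also be censored". Section 14.4 also counts death in the primary PFS.

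**The concern.** A man who dies without ADT has not started ADT, so the rule in 9.5.5 censors him. Followed exactly, the plan produces a curve labelled survival that does not respond to mortality. That does not match the rationale in section 4.5, which gives longer survival without starting ADT as a goal of the treatment. A man who has died can no longer start ADT, so censoring him answers a hypothetical question about ADT timing in the absence of death.

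The objective in section 3.3 sets SABR against SABR + Radium-223. Only one arm adds radium-223, and section 14.3 monitors grade 4/5 toxicity in that arm. If deaths before ADT differed between the arms, the reported ADT-FS curves would not show it.

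**Working it through.** The plan gives no sample size, power or event count for ADT-FS, so there is no stated figure to reproduce. The check has three parts.

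**1. Treatment of death by endpoint**

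| Endpoint | Event | Death |
|---|---|---|
| PFS (9.5.5, 14.4) | progression composite or death | event |
| OS (9.5.5) | death | event |
| Time to progression (9.5.5) | tumor progression, new lesions or ADT | explicitly censored |
| ADT-FS (9.5.5, 14.1.2) | ADT initiation | not mentioned; censored under the general rule in 9.5.5 |

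**2. Size of the effect**

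Inputs:
- ADT-start median of 21 months, from the metastasis-directed arm of the trial cited in section 4.5. The protocol does not say how that trial handled death, so using the figure as a pure ADT-start median is an assumption.
- 32 men per arm and 24 months of follow-up (14.2).
- 24-month death risk *d*. The documents give none, so it is assumed, over the range 3-20%.
- Constant, independent hazards for ADT start and for death (assumed).

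Formulas:
- λ_A = ln 2 / 21 = 0.0330 per month; λ_D = −ln(1 − d) / 24.
- Deaths censored: S(24) = 2^(−24/21) = 0.453 and median 21.0 months, for every *d*.
- Deaths counted: S(24) = 0.453 × (1 − d); median = ln 2 / (λ_A + λ_D).
- Deaths before ADT per 32 men = 32 × λ_D/(λ_A + λ_D) × (1 − S(24)), with S(24) from the deaths-counted line.

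Example, d = 5%: λ_D = 0.0513/24 = 0.00214. S(24) = 0.453 × 0.95 = 0.430. Median = 0.693/0.0351 = 19.7 months. Deaths before ADT = 32 × 0.0608 × 0.570 = 1.1.

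| Assumed d | 24-month estimate, censored | 24-month estimate, counted | Median, censored | Median, counted | Deaths before ADT per 32 |
|---|---|---|---|---|---|
| 3% | 45.3% | 43.9% | 21.0 | 20.2 | 0.7 |
| 5% | 45.3% | 43.0% | 21.0 | 19.7 | 1.1 |
| 10% | 45.3% | 40.8% | 21.0 | 18.5 | 2.2 |
| 20% | 45.3% | 36.2% | 21.0 | 16.4 | 4.5 |

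For scale, the expected number of ADT starts by 24 months without deaths is 32 × (1 − 0.453) = 17.5. One death is about 6% of that (1/17.5).

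**3. What a censored death does to the curve**

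Place 32 ADT times at the quantiles of the same distribution: 6 fall before month 6 and 18 before month 24. Let one man who would have stayed free of ADT through month 24 die at month 6.
- No death: 14/32 = 0.438.
- Death censored: 26/32 × 13/25 = 0.423.
- Death counted: 26/32 × 25/26 × 13/25 = 13/32 = 0.406.

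The censored death gives a higher estimate than the counted death, but here a lower one than if the man had lived on without ADT.

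**The case against.** Several points on the other side stand.

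- **Mechanism.** A reader might infer that a man who dies before ADT helps his arm by being carried forward as a success. He is not: he leaves the risk set. Under independent censoring the expected curve is the same as with no deaths. The overstatement exists only relative to an endpoint that counts death.
- **Explicit wording.** The sentence in 9.5.5 that censors death belongs to time to progression, not to ADT-FS. For ADT-FS, censoring follows from the general rule.
- **Comparison between arms.** The objective is worded as one arm versus the other, but 14.5 plans only curves and medians. No alpha or power is attached, so no formal conclusion depends on this endpoint.
- **Hidden toxicity.** Fatal toxicity would not go unseen. PFS counts death, 14.3 has its own stopping rule for the radium arm, and 9.5.5 defines OS (although 14.5 plans no summary of it).
- **Few deaths are likely.** Section 5.1 says "Patient must have a life expectancy" of at least 12 months and asks for asymptomatic lesions, 5.2 excludes castration-resistant disease, and 14.2 says "Patients will be followed for 2 years after Day One of trial or until death". Nothing in the documents supports the 20% row of the table.
- **Choice of estimand.** Section 4.5 also values deferral of ADT in itself, and time to ADT is a legitimate quantity. If that is what is meant, the label is wrong rather than the event.

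A reader might also expect the result to be set beside the ADT-free survival of the cited trial. No section plans that, and the protocol does not report how that trial treated death.

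These points limit the size and reach of the concern. They do not remove it: under the written rule an endpoint named survival ignores mortality, and Kaplan-Meier with deaths censored does not estimate the proportion alive without ADT.

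**Conclusion.** The concern holds as a defect of definition in a secondary endpoint. As written, ADT-FS is time to ADT with deaths censored, and it is overstated relative to a death-inclusive endpoint in any arm with deaths before ADT. For an assumed 24-month death risk of 3-5%, the overstatement is 1.4 to 2.3 percentage points at 24 months and 0.8 to 1.3 months on the median. At 10% it is 4.5 points and 2.5 months. These figures rest on the 21-month ADT median, constant independent hazards and assumed death risks. If death and ADT start are correlated, the censored curve could also be biased as an estimate of time to ADT, in a direction that the documents do not settle.

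The documents do not support the stronger reading that the plan rewards toxic deaths or threatens the trial's main conclusion. The primary PFS and its sample size are unaffected.

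**What to change.** In sections 9.5.5 and 14.1.2, define ADT-FS as the time from randomization to ADT initiation or death from any cause, whichever comes first, with men alive and without ADT censored at last contact. This also removes the conflict over the time origin. If time to ADT is the intended quantity, rename the endpoint accordingly in both sections, use a single time origin, and in 14.5 report cumulative incidence with death as a competing event. Both quantities can be reported if wanted.

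The cost is about one sentence in each of two sections, plus one in 14.5 if the competing-risk route is taken. Death dates are already needed for PFS and OS, so no new data are required. Under the death-inclusive definition, ADT-FS estimates may be slightly less favourable. Make the change before the analysis and without reference to outcomes by arm.
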